## **7. Determination of statistical non-inferiority**

The first comparison to be tested will be the MPa200Z 6 month experimental regimen against the standard regimen. The second comparison to be tested will be the MPa200Z 4 month experimental regimen against the standard regimen. The third comparison to be tested will be the MPa100Z 4 month experimental regimen against the standard regimen. To preserve the type I error rate, the second comparison will only be tested if non-inferiority is demonstrated with the 6 month experimental regimen. Similarly the third hypothesis will only be tested if non-inferiority of the PA-824 200mg 4 month regimen has been demonstrated. This strategy means no adjustments are required for multiple comparisons.

Non-inferiority will be assessed using the upper bound of the two-sided 95% confidence interval for the difference between the proportion of participants who are classified as having an unfavourable status on the intervention and the control regimen.

If the upper bound of the two-sided 95% confidence limit for the difference, proportion with unfavourable status on intervention arm less the proportion with unfavourable outcome on the control arm, is less than 12% (the margin of non-inferiority) the intervention will be considered to be non-inferior to the control arm on that comparison.

The PP and MITT analyses will be considered primary. However, in order to declare an intervention to be non-inferior, consistent results should be obtained from the ITT analysis and from sensitivity and subgroup analyses, although not all of these will necessarily satisfy the strict definition of non-inferiority.

All primary efficacy analyses of the three main analysis populations will be adjusted for HIV status and cavitation, using a stratified analysis of the risk difference from each stratum using Cochran-Mantel-Haenszel weights.

When interpreting the results, particularly if they are close to the margin, the STAND study team will weigh all the data including the unfavourable rates with their component parts, safety and adherence in considering the benefit of any experimental arm(s). However, if the control arm unfavourable rate is observed to be much lower than what is anticipated we acknowledge there may be difficulty in interpreting the results and there may be situations where it may not be possible to draw positive conclusions from the trial. A table and commentary of hypothetical observed results with variable N assessable and % unfavourable in the control arm is given Appendix 1.

## **8. Sensitivity analyses of primary endpoint analysis**

In addition to analysing the primary endpoint data by per protocol and MITT and ITT, it is planned to conduct the following sensitivity analyses:

1. An analysis of all randomised patients
2. An analysis of the ITT population, with missing outcomes data treated as unfavourable
3. An analysis of the ITT population, with missing outcomes data treated as favourable

4. An analysis of the ITT population, with missing outcomes data treated according to status at the last observation (last two samples)
5. An analysis of patients in the MITT and PP populations where reinfections are classified as unfavourable outcomes
6. An analysis of the MITT and PP populations treating all deaths as unfavourable
7. An analysis of the MITT population in which patients who changed treatment for reasons other than failure or relapse were classified according to their status at the end of follow-up.

In these sensitivity analyses, reinfections are considered as missing outcome data (except for point 5).

## **9. Secondary efficacy analyses of primary endpoint**

### **9.1. Unadjusted results**

Unadjusted difference in the proportion of unfavourable for each pairwise comparison (intervention arm-control arm) with 95% confidence intervals will be presented.

### **9.2. Additional covariate adjustment**

Additional baseline covariates listed in section 6 will be considered for a secondary adjusted analysis for the primary endpoint. This will be a secondary analysis, assuming baseline covariates are well balanced across the treatment arms.

### **9.3. Time to event unfavorable outcome analysis**

Time to an unfavourable outcome will be analysed with Kaplan Meier plots and Cox's proportional-hazards regressions analysis. These analyses will be performed according to PP, MITT and ITT endpoint classifications. Patients withdrawn from the study during treatment will be censored at the time last seen in the study and classified as having an unfavourable endpoint at that time. Those changing treatment or restarting treatment for whatever reason will be classified as having an unfavourable endpoint at the time of change. Patients lost during the follow-up phase who have not already been classified as having an unfavourable endpoint will be classified according to their status at the time they are last seen, thus a patient who had not yet achieved culture negative status, or a patient with a positive culture even of a low colony growth not followed by two negative cultures would be classified as having attained an unfavourable endpoint.

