#### **4.4. Lost to Follow-up or Early Withdrawal**

Lost to Follow-up or Early Withdrawals *before* the end of the treatment (month 4 or 6) are considered as unfavourable outcomes for ITT and MITT. However these patients will be excluded from the Per Protocol analysis. The MITT and Per Protocol analyses will consider Lost to Follow-up *after* end of treatment (month 4 and 6) as unassessable unless at the time of default from follow-up the patient a) was already classified as having an unfavourable outcome, b) did not have culture negative status, or c) had a positive culture result (“isolated positive culture”) not followed by at least two negative culture results at different visits (at least 7 days apart), in which cases the patient will be classified as having an unfavourable outcome. We believe this is the most appropriate approach for the primary analysis because together with the non-tuberculosis deaths, this group is likely to considerably out-number the bacteriological failures and relapses. These patients will be considered as having an unfavourable outcome in the ITT analysis.

There is a clear precedent for this analytic approach in other TB trials, and these trials also provide examples of why the inclusion of the losses to follow-up as unfavourable greatly affects the results.

Data from the Priftin trial which led to accelerated approval of rifapentine and a trial conducted by the International Union Against TB & Lung Disease (IUATLD) in African and Asian sites illustrate the problems associated with classifying all losses to follow-up and deaths as having an unfavourable outcome.

In the Priftin trial bacteriological relapses occurred in 5% of patients on the rifampicin based regimen compared to 11% on the rifapentine based regimen. Approximately one third of patients were lost to follow-up and when this group combined with patients unassessable for other reasons were added to the bacteriological failures, the rates increased to 53% and 57% respectively. The true bacteriological relapses were greatly outnumbered by these other groups. At the time of the licensing submission to the FDA it was recognised that because there were a substantial number of patients likely to be unassessable the main focus should be on the relapse rates. In the final statistical report the results were first reported excluding those unassessable and then assuming all losses had an unfavourable outcome and finally assuming all losses had a favourable outcome.

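### Section 9.3 claims to follow the ITT classification, but its follow-up-loss rule makes culture-negative losses non-events although ITT counts them as unfavourable

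*SAP*

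**What the plan says.** Section 9.3 opens with a general statement: "These analyses will be performed according to PP, MITT and ITT endpoint classifications". It then gives three rules without separating the populations:

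- Patients withdrawn during treatment "will be censored at the time last seen in the study and classified as having an unfavourable endpoint at that time".
- On treatment changes: "Those changing treatment or restarting treatment for whatever reason will be classified as having an unfavourable endpoint at the time of change".
- Patients lost during follow-up and not already unfavourable "will be classified according to their status at the time they are last seen". The rest of that sentence names who becomes an event: those not yet culture negative, and those with a positive culture not followed by two negatives.

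Section 4.4 deals with the same patients by population. Losses before the end of treatment "are considered as unfavourable outcomes for ITT and MITT" and are left out of PP. For MITT and PP, losses after the end of treatment are treated "as unassessable unless at the time of default from follow-up the patient a) was already classified as having an unfavourable outcome", or lacked culture negative status, or had an unresolved positive culture. For ITT, section 4.4 says of the losses after treatment: "These patients will be considered as having an unfavourable outcome in the ITT analysis". Section 6.1.2 agrees, since anyone without a favourable 12-month outcome is unfavourable, and 6.1.1 requires negative culture status at weeks 50 to 54.

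**The concern.** A time-to-event analysis needs one coding per patient: event or censored, with a date. For ITT, the opening sentence of 9.3 and its follow-up-loss rule give different codings for the same patient. A programmer who follows the detailed rule produces an ITT curve that leaves out a whole component of the ITT endpoint, and it will disagree with the ITT risk difference reported beside it.

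The group concerned is not expected to be negligible. Section 4.4 says of follow-up losses, taken together with non-tuberculosis deaths, that "this group is likely to considerably out-number the bacteriological failures and relapses". Section 7 also says the study team will weigh all the data when a result lies close to the margin, so a mislabelled ITT hazard ratio could enter that discussion.

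**Working it through.** **1. The rules side by side**

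| Patient | 9.3 | ITT | MITT | PP |
|---|---|---|---|---|
| Lost in follow-up, culture negative, treatment completed | Non-event | Unfavourable (4.4, 6.1.2) | Excluded (4.2 item 1) | Excluded |
| Lost in follow-up, not culture negative or unresolved positive | Event | Unfavourable | Unfavourable | Unfavourable |
| Lost or withdrawn during treatment | Called both censored and unfavourable | Unfavourable (4.4, 6.1.2) | Unfavourable (6.1.3 item 8) | Excluded unless already unfavourable (4.3 item 1) |

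The first row holds the conflict, and it lies in the ITT column. In MITT and PP these patients are not in the analysis, so the 9.3 rule contradicts nothing there.

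**2. Inputs from Appendix 1, and a check of its own figure**

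Control unfavourable rate 16%, unassessable 15%, isoniazid mono-resistance 8%, margin 12%, power 90%, one-sided 2.5%.

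n = 2 × 0.16 × 0.84 × (1.960 + 1.282)² / 0.12² = 196.1 assessable per arm.
196.1 / (1 − 0.15 − 0.08) = 254.7, so 255 per arm, as the SAP states.

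Both rates are therefore shares of those randomised. With 300 per arm, ITT is about 300 × 0.92 = 276, ignoring the other late exclusions in 4.1. Culture-negative follow-up losses cannot exceed the planned unassessable share, 15/92 = 16.3% of ITT, or 45 patients. That is a planning ceiling and not an estimate, because unassessable patients include other groups. The actual share L is not given, so 5, 10 and 15% are shown as assumptions.

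**3. ITT proportion by classification:** L + (1 − L) × 0.16

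- L = 0.05: 0.05 + 0.95 × 0.16 = 20.2%
- L = 0.10: 0.10 + 0.90 × 0.16 = 24.4%
- L = 0.15: 0.15 + 0.85 × 0.16 = 28.6%

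**4. Kaplan-Meier estimate under 9.3**

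Assumed timing: events uniform over months 0 to 12, losses censored uniformly over months 6 to 12. On-treatment withdrawals are coded as events. Let a = (1 − L) × 0.16 / 12 and c = L / 6 (both per month). The share at risk at month 6 is Y6 = 1 − 6a, and at month 12 it is Y12 = Y6 − 6(a + c). Then

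estimate = 1 − Y6 × (Y12 / Y6)^(a / (a + c)).

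For L = 0.15: a = 0.01133, c = 0.025, Y6 = 0.932, Y12 = 0.714, exponent 0.312, giving 1 − 0.932 × 0.920 = 14.2%.

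| L (assumed) | Patients per arm coded differently (of 276) | ITT by classification | ITT curve under 9.3 |
|---|---|---|---|
| 5% | 14 | 20.2% | 15.4% |
| 10% | 28 | 24.4% | 14.8% |
| 15% | 41 | 28.6% | 14.2% |
| 16.3% (ceiling) | 45 | 29.7% | 14.1% |

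At the ceiling, 45 patients are coded non-events, against 0.16 × 231 = 37 coded events.

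Timing matters little. With all events on treatment or all in follow-up, the 9.3 figures for 5, 10 and 15% range over 15.2–15.6, 14.4–15.2 and 13.6–14.8%. With losses starting at month 4 they are 15.5, 15.0 and 14.4%.

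**5. Hazard ratio**

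Same timing, equal losses in both arms, and an assumed 16% against 20% unfavourable among those not lost. The large-sample Cox solution for losses of 5, 10 and 15% is 1.22, 1.18 and 1.15 when losses count as events, and 1.28 throughout under 9.3.

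**The case against.** The best defence is that the 9.3 rule is a reasonable analysis. Section 8 item 4 already plans an ITT-population analysis by status at last observation, and 4.4 explains why counting losses as unfavourable hides true failures. With equal losses, the hazard ratio also stays near 1.28 under 9.3, while counting losses as events pulls it towards 1, which is the less cautious direction in a non-inferiority trial. This stands as a reason to keep the analysis. It does not justify calling it the ITT classification.

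A second defence is that 9.3 never says culture-negative losses are censored, so its opening sentence could govern. That reading is possible, but the list of which losses become events makes non-event status the more natural one. If both readings are open, the text still needs fixing.

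Three stronger readings are tempting and are not supported:

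- *On-treatment withdrawals would be lost as events.* The word *censored* is the wrong technical term, but the rest of its own sentence assigns an unfavourable endpoint, and 4.4 and 6.1.3 item 8 agree. It is loose wording.
- *The conflict affects all three populations.* For patients who completed treatment it is confined to ITT. A patient lost in follow-up after inadequate treatment is unassessable under 4.4 but unfavourable under 6.1.3 item 7. That clash is mainly between those two sections, and the SAP gives no figure for its size.
- *The treatment-change rule miscounts many MITT and PP patients.* It omits the exceptions in 6.1.3 item 6 and the restriction in 6.1.4 item 6, but 4.2 items 2 and 5 and 4.3 item 2 already remove most of those patients.

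**Conclusion.** The point holds for ITT. Section 9.3 says it follows the ITT classification, and its follow-up-loss rule does not. The gap between the ITT proportion and the curve labelled ITT is about 5, 10 and 14 percentage points at 5, 10 and 15% culture-negative losses. Those shares, the event timing and the use of 16% among patients not lost are assumptions; the direction of the gap does not depend on them.

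A reader might infer that the trial's conclusion is at risk. The documents do not support that. Section 7 decides non-inferiority on the stratified risk difference, with PP and MITT primary, and 9.3 is a secondary analysis. Losses also remain visible in the ITT risk difference and in section 8 items 2 to 4. The text should be corrected before analysis because the ITT label would mislead.

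**What to change.** Amend 9.3 in three places:

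- **(a) ITT events.** State that for ITT any patient unfavourable under 6.1.2 is an event. Date it at the last visit for losses and withdrawals, at death for deaths, and at the 12-month visit (or last visit if there was none) for patients with no usable 12-month culture. Keep status when last seen only as a separately labelled sensitivity analysis. Alternatively, state explicitly that the time-to-event analysis departs from the ITT classification. Give the matching dates for the 24-month repeat in 10.1.
- **(b) Withdrawals during treatment.** Replace the wording that both censors these patients and gives them an endpoint. Say that in ITT and MITT they count as events at the date last seen, and that 4.3 item 1 excludes them from PP unless already unfavourable.
- **(c) Treatment changes.** Keep the sentence, but make it subject to the exclusions and exceptions in 4.2, 4.3, 6.1.3 item 6 and 6.1.4 item 6. State whether a treatment change is an ITT event. Sections 6.1.1 and 6.1.2 do not mention it, so simply deleting the sentence could drop a changed-treatment patient who is culture negative at 12 months.

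Separately, reconcile 4.4 and 4.2 item 1 with 6.1.3 item 7 for patients lost in follow-up after inadequate treatment.

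The cost is SAP wording only, with no change to data collection, sample size or the primary analysis.

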### **9.4 Status at end of treatment**

Status at end of treatment based on assessable patients based on culture result at end of chemotherapy, 4 or 6 months, using the penultimate month culture if the culture result at end of chemotherapy is unavailable will be compared across randomised groups.

### **9.5 Status at 12 months in those who are favourable at end of treatment**

Status at 12 months after the start of therapy in those patients who have a favourable response at the end of treatment and are assessable at 12 months or have already met the definition of unfavourable response.

## **10. Secondary efficacy endpoints**

### **10.1. Incidence of bacteriologic failure or relapse at 24 months**

Efficacy analyses as described for the 12 month endpoint will be repeated for the 24 month endpoint.

### **10.2 Rate of change in time of sputum culture positivity (TTP)**

Speed of decline of sputum viable counts as assessed by non-linear mixed effects (NLME) modelling of the time to positivity (TTP) in MGIT will be performed by the Statistics Team performing the safety analyses for STAND. Details of this will be documented elsewhere.

### **10.3 Time to sputum culture conversion to negative status**

Time to culture negative status (first of two negative cultures without an intervening positive culture) will be analysed using survival analysis techniques, Kaplan Meier plots and Cox proportional hazard regression.

### **10.4. Culture conversion status at 4, 8, 12 and 17 weeks**

Patients will be classified as being culture positive, culture negative, dead or unassessable at 4, 8, 12 and 17 weeks. Every effort will be made to obtain a sputum sample from all patients but it is recognised that some patients may not have produced any sputum in the preceding week and may be unable to do so when requested. Patients who cannot produce sputum will be classified as being culture negative at that time point. The proportion culture negative will be those classified as being culture negative divided by the total considered culture negative, culture positive or have died.

In a separate sensitivity analysis patients who are unassessable at this time point for whatever reason (e.g. culture contaminated) will be considered to be culture positive unless they are culture negative on at least two previous assessments in which case they will be considered to be culture negative. This does not include patients who could not produce sputum at 4, 8, 12 and 17 weeks, who are considered to be culture negative.

Differences from the control regimen in culture negativity at weeks 4, 8, 12 and 17 will be expressed as a difference in proportions with corresponding 2-sided 95% confidence intervals.

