### 3. Definitions and data handling issues

#### 3.1. Definitions

**Positive culture** refers to the culture being positive for M.tb. N.B.: In the absence of the speciation data, the unconfirmed result will be treated as positive for M.tb. False positive or contaminated will be treated as missing. Specimens classified as non-tuberculous mycobacteria (NTM) and negative for M.tb will be treated as contaminated (adequate conditions for growth of M.tb exist if NTM grow). The bacteriology algorithm for reporting MGIT results can be found in STAND Laboratory Manual. Two sputum samples per visit are collected at each visit throughout treatment and follow-up. The culture result for a given visit is established using all samples obtained for that visit. A positive culture takes precedence over a negative culture at the same visit.

**Culture negative status** is achieved when a patient produces at least 2 negative culture results at different visits (at least 7 days apart) without an intervening positive culture result for M.tb. The date of the first negative culture of these two is the date at which culture negative status was obtained. Once obtained, culture negative status continues until there are two positive cultures at different visits (at least 7 days apart), without an intervening negative culture, or until there is a single positive culture not followed by two negative cultures. Culture negative status can be achieved at any time during treatment or follow-up but before any re-treatment and can be re-established.

Patients with two contaminated or missing samples at a given visit (from Month 2 onwards) will be asked to return to produce two more sputum samples. A single culture result or inability to produce sputum (see section 3.2) at 12 months will be sufficient to count that patient as having data for primary endpoint classification.

**Treatment failure or Bacteriologic failure** is defined as being declared an unfavourable status (as defined in section 6) at or before the end of treatment (either 4 or 6 months) or failing to attain culture negative status and being declared an unfavourable outcome.

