#### **4.2. Additional exclusions from MITT analysis**

1. Patients who, having completed treatment, are lost to follow-up or withdrawn from the study, their last status being culture negative and their last positive culture result (“isolated positive culture”) followed by at least two negative culture results at different visits (at least 7 days apart, without an intervening positive culture)
2. Women who become pregnant during treatment and stop their allocated treatment
3. Patients who died during treatment from violent or accidental cause (e.g. road traffic accident). N.B.: This does not include death from suicide, which will be considered an unfavourable outcome.
4. Patients who died during follow-up (after the end of treatment) with no evidence of failure or relapse of their TB, their last status being culture negative and their last positive culture result (“isolated positive culture”) followed by at least two negative culture results at different visits (at least 7 days apart), and who have not already been classified as unfavourable.
5. Patients who, after being classified as having culture negative status, are re-infected with a new strain from that with which they were originally infected. Reinfection will be defined specifically as a patient infected with a strain that is genetically different from the initial strain (see Mycobacteriology Laboratory Manual).
6. Patients who are able to produce sputum at 12 months, but whose 12-month visit sputum samples are all contaminated or missing, who cannot be brought back for repeat cultures, provided they have not already been classified as unfavourable and provided their last positive culture was followed by at least two negative cultures. N.B.: This does not apply to patients who are unable to produce sputum at 12 months, or to patients who are able to be brought back subsequently and produce negative cultures.

Patients in categories 1-5 above who had already been classified as having an unfavourable outcome will not be excluded.

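### The Section 10.4 sensitivity rule scores an unassessable patient culture negative after any two earlier negatives, even when a positive has followed them

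*SAP*

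**What the plan says.** SAP Section 10.4 sorts patients into four states at each time point: "Patients will be classified as being culture positive, culture negative, dead or unassessable at 4, 8, 12 and 17 weeks". The main analysis leaves unassessable patients out of the denominator. A separate sensitivity analysis puts them back in: "patients who are unassessable at this time point for whatever reason (e.g. culture contaminated) will be considered to be culture positive". One exception is attached to that default, and it turns on the patient's history: "unless they are culture negative on at least two previous assessments in which case they will be considered to be culture negative". Patients unable to produce sputum are outside this rule, because they already count as negative.

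Other parts of the SAP that turn a run of cultures into a status take account of positives:

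- Section 3.1 defines culture negative status as "at least 2 negative culture results at different visits (at least 7 days apart) without an intervening positive culture result for M.tb". The status ends with two successive positives, "or until there is a single positive culture not followed by two negative cultures".
- Section 10.3, the neighbouring time-to-conversion endpoint, uses the "first of two negative cultures without an intervening positive culture".
- Section 4.2 item 6 covers contaminated or missing samples at 12 months and excludes the patient from MITT only "provided their last positive culture was followed by at least two negative cultures".
- Section 4.4 (c), Section 6.1.1, Section 6.1.3 item 3 and Section 9.3 also ask whether the last positive was followed by two negatives.

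**The concern.** The exception in 10.4 counts negatives but ignores their order. Two negatives anywhere in the history are enough, whatever came after them, so a patient whose most recent culture is positive can be imputed as negative when the next culture is contaminated or missing.

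This sits badly in an analysis whose default for a missing result is culture positive. The patients for whom that default is most plausible, those with a recent positive, can be moved to the negative group by older results.

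The clause can also be programmed in several ways: any two earlier negatives, the last two results, or 3.1 status. It does not say whether previous assessments means the 10.4 time points or all earlier visits. These choices give different counts.

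**Working it through.** The SAP states no figure for this rule, so there is none to reproduce. The check sets the 10.4 exception beside the condition used elsewhere.

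**Inputs.** Each earlier assessable result is negative (N) or positive (P), in time order.

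- Literal 10.4 rule: negative if the history holds at least two N in any position.
- Comparison rule, as in 4.2 item 6: negative if the history ends in at least two N, so that no positive follows them.

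**Only the 10.4 time points count as previous assessments.**

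- Week 4: no earlier result, so the exception cannot apply.
- Week 8: one earlier result, so it cannot apply.
- Week 12: two earlier results. Only NN qualifies, and both rules agree.
- Week 17: three earlier results and 2 × 2 × 2 = 8 possible histories. Four hold at least two N: NNN, PNN, NNP and NPN. The first two end in two negatives. The other two do not, and NNP ends in a positive.

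NNP is the patient who is negative at weeks 4 and 8, positive at week 12 and contaminated at week 17. The literal rule scores this patient negative at week 17.

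**Other visits count too.** Three or more earlier results can then exist before week 17, so the conflict can arise sooner. With four earlier results there are 16 histories, and the literal rule scores 6 + 4 + 1 = 11 of them negative (two, three or four N). Four of the 11 end in two negatives. The other 7 do not: NNNP, NNPN, NNPP, NPNP, NPPN, PNNP and PNPN. Four of these 7 end in a positive, and one (NNPP) ends in two.

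These are counts of possible patterns, not of patients. They show where the rules part, not how often.

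**Weight of one patient.** With 300 randomised per arm, one reclassified patient moves that arm's proportion by 1/300 = 0.33 percentage points. After removing the 8% assumed in Appendix 1 for isoniazid mono-resistance, the denominator is 300 × 0.92 = 276 and the shift is 1/276 = 0.36 points. The SAP gives neither the unassessable rate at these time points nor the share of such patients with a late positive, so no total follows.

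**The case against.** **The authors may have meant the last two assessments.** Possibly, but the text does not say so. The SAP is explicit elsewhere when it means that: Section 3.3 and Section 10.5 use the word consecutive, and Section 8 item 4 specifies the last two samples. Reading culture negative as 3.1 status does not help either, since status held at two earlier assessments can since have been lost.

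**Section 3.1 does not clearly contradict the result.** This stands in part. A reader might infer that every patient in the conflicting patterns has lost 3.1 status. But 3.1 and 3.3 also use later results. A patient with N, N, P, contaminated, N, N keeps the status throughout, and one with N, P, N, contaminated, N attains it from the negative just before the missing visit. In those cases scoring the gap as negative agrees with 3.1 in hindsight. The defect is that the 10.4 rule ignores a later positive on the results then available, not that it always contradicts 3.1.

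**Little depends on it.** This stands. It is a sensitivity analysis of a secondary endpoint, reported as differences with confidence intervals and with no margin. The sensitivity analyses of the primary endpoint are listed in Section 8, and 10.4 is not among them. Two samples are taken per visit, and Section 3.1 recalls patients with two contaminated or missing samples from Month 2 onwards, which should reduce the number unassessable at the later time points.

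**Stronger readings that the SAP does not support.**

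- A reader might infer that the rule favours a regimen with early suppression and later regrowth. Nothing in the SAP shows that reversion or missing cultures would differ between arms, and the same pattern in both arms would partly cancel.
- A reader might attach a size: 10% unassessable, of whom 5% to 20% have a late positive, gives 0.10 × 0.05 = 0.5 to 0.10 × 0.20 = 2 points in one arm. Neither rate is in the SAP.
- A reader might take the analysis to be the plan's declared strict check on missing data. The SAP calls it only a separate sensitivity analysis.

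**Conclusion.** The point holds as a wording defect of minor weight. As written, the 10.4 exception would score some unassessable patients culture negative when their latest available result is positive, or when their last positive has not been followed by two negatives. This departs from the condition the SAP applies elsewhere, including to contaminated or missing 12-month samples in Section 4.2 item 6.

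Whether the conflict is confined to week 17 depends on which visits count as previous assessments, and the SAP does not say. One such patient is worth roughly a third of a percentage point in one arm. The number of such patients cannot be derived from the document and is probably small, and the direction of any effect on the difference between arms is unknown. The primary endpoint and the non-inferiority decision are untouched.

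**What to change.** In Section 10.4, replace the exception with: *unless their two most recent assessable visits before that time point (at least 7 days apart) were both culture negative, with no later positive culture*. Add that all earlier scheduled visits count as previous assessments, not only weeks 4, 8 and 12.

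This still forgives an isolated positive once two negatives have followed it. It is a backward-looking imputation rule in line with Section 4.2 item 6. It should not be labelled as 3.1 culture negative status, because 3.1 also uses results obtained after the time point.

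The cost is one clause and one sentence in the SAP, and the matching lines of code. It needs no new data.
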